Randomization will be generated using a SAS program based upon permuted random blocks of variable size to assure approximate balance over time and will be stratified by sex and statin use.

Aim 1a: *a) We hypothesize that exercise training will result in a decrease in Left ventricular end diastolic and end systolic volume and increase in ejection fraction (measures of morphology and systolic performance) as compared to the control group. b) We hypothesize that exercise training will increase mitral annular early diastolic velocity (e') as well as decrease the ratio (E/e') of early mitral inflow velocity (E) and e' (measures of diastolic performance). c) We hypothesize that both forms of training will be more beneficial compared to the control group and IMT will be non inferior to aerobic training regimen as related to cardiac remodeling.*

The outcomes for these hypotheses will be the outcome measures at baseline and at the end of follow-up. Parts a & b involve superiority tests using a mixed linear regression model comparing each active treatment group to the control group, specifically the interaction between time and treatment, with the ability to adjust for baseline values of the outcomes. Part c requires a test of non-inferiority between the two active treatments also involving a mixed model with a lower bound of 0.65 standard deviation units for each measure [see Sample Size and Power below].

Aim 2. *To explore the benefits of improved cardiac remodeling and physiology on functional and qualitative exercise training endpoints. a) We hypothesize that exercise training related cardiac improvements will lead to improved aerobic functional parameters (measured as peak VO_2 and VE/VCO_2 slope). b) We hypothesize that exercise training-related cardiac improvements will lead to improved quality of life.*

For hypotheses a & b, baseline and follow-up in peak VO_2 , VE/VCO_2 slope and quality of life will be the outcomes in separate mixed linear regression models using the measures of morphology, systolic and diastolic performance at evaluation times that were used as outcomes in aim 1 as predictors.

Exploratory Aim. Using the outcomes from aim 2 in separate mixed linear regression models using the predictors from aim 1 with the addition of potential confounders of peripheral function as determined by the supporting funded Merit to. We will evaluate the independent effect of central cardiac change on function.

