Sample Size and Power: With respect to superiority testing for mixed models in **aim 1**, power for an equivalent t-test will be used with sample sizes of 30 for the active treatment and 15 in the control group. This will result in the ability to detect a difference of 0.91 standard deviation [SD] units with 80% power, assuming an alpha level of 5%. For non-inferiority testing in aim 1, we propose a detectable difference of zero, with a lower boundary of 0.65 SD units, which provides 80% power using an alpha level of 5%⁷⁹.

In **aim 2**, a mixed linear regression model with 7 predictors would result in a detectable R^2 of 0.19 compared to a null model with 80% power, assuming alpha=5% and 75 subjects.

Study Data Management and Quality Control:

Prior to the initiation of the study, all investigators and research staff involved in clinical activities will meet to review study procedures and will complete all required trainings on data and patient privacy procedures. Documentation of any protocol breaches will be required. Each protocol violation will be evaluated by the PI and a determination made regarding the validity of any justification for the violation.

The study databases will be located at the VABHS. The clinical database with all research data will be stored on VA network drives and housed behind the VA firewall on VA owned and maintained servers, which are backed up on a regular schedule. All computers will have Kerberos passwords and come equipped with antivirus software. Data will not be stored on desktops or on non-VA servers. Study data will be coded with a unique study identifier for each participant and stored in a de-identified manner. A study data set without identifiable information will be used for all data analysis. Identifiable information will be collected for patient tracking and safety purposes, but will only be kept for as long as the study is active. De-identified clinical data will be stored separately from the participant's name, contact information, and real SSN. Access to the cross-walk file linking the participant's identifiers and their study data will be restricted to the project manager. This file will be destroyed according to CSP policy after the study ends. Study data will be retained and stored after the study ends according to federal and local VA regulations. Access to the study data is heavily restricted to

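### Aim 1 leaves open using the baseline echo value as both response and covariate; fix one model per contrast that uses baseline once

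*Combined protocol and SAP*

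**What the plan says.** Under Statistical Analysis, Aim 1, the plan defines the response: "The outcomes for these hypotheses will be the outcome measures at baseline and at the end of follow-up". Parts a and b compare each training arm with control in a mixed linear regression model. The tested term is "specifically the interaction between time and treatment, with the ability to adjust for baseline values of the outcomes". Part c uses a mixed model for non-inferiority of IMT to aerobic training, with a bound of 0.65 SD.

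The text does not say when the baseline adjustment would be used or in what form. It gives no covariance structure and no degrees-of-freedom method.

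The randomisation paragraph says that allocation "will be stratified by sex and statin use". Neither factor is named in the Aim 1 model. The paragraph before Exercise Training shows that only aerobic versus IMT is randomised, within the parent Exercise Therapy study. Under Recruitment, controls are found separately through flyers, mailings and clinics.

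Under Sample Size and Power, "power for an equivalent t-test will be used" with "sample sizes of 30 for the active treatment and 15 in the control group", giving "the ability to detect a difference of 0.91 standard deviation [SD] units".

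**The concern.** With one pre and one post measurement, the baseline value is already half of the response data. Adding it as a covariate to that model regresses baseline on itself at the first visit. The interaction estimate does not move, but the residuals on which its standard error rests are distorted.

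Leaving the covariate out gives a sound test. It does not exploit the correlation between visits as fully as baseline adjustment would, and precision is scarce in contrasts of 30 versus 15 and 30 versus 30.

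Because the adjustment is only an ability, it could also be exercised after results are seen, separately for each of the five measures named in the Aim 1 statistical text (end-diastolic volume, end-systolic volume, ejection fraction, e', E/e').

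**Working it through.** **Inputs from the plan.** Arms of 30, 30 and 15; two visits 12 weeks apart; 80% power; alpha 5%.

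**Assumptions.** The plan gives no correlation r between visits, so r = 0.3 to 0.9 is shown. Variance is equal (set to 1) at both visits.

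**The plan's own figures.** A two-sample t-test, 30 versus 15, two-sided 5%, has 80.3% power at 0.91 SD, and its detectable difference is 0.906 SD. For non-inferiority, 30 versus 30 with a 0.65 SD bound and true difference zero gives 80.0% power at one-sided 5%. Both figures reproduce.

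**Option taken: baseline as response and covariate.**

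1. The covariate has the same value at both visits, so it cancels from follow-up minus baseline. The time-by-treatment estimate is unchanged, and its true variance is proportional to 2(1−r).
2. The slope pooled over visits is b = (1+r)/2.
3. Residual variance at baseline: (1−b)² = (1−r)²/4.
4. Residual variance at follow-up: 1 + b² − 2br = 1.25 − 0.5r − 0.75r².
5. Residual covariance: (1−b)(r−b) = −(1−r)²/4. This is negative, so a random-intercept variance bounded at zero is pushed to zero.
6. The model variance is then the sum of steps 3 and 4: 1.5 − r − 0.5r² = (3+r)(1−r)/2.
7. Model SE / true SE = √[(3+r)/4].

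The approximate type I error is 2[1 − Φ(1.96 × ratio)]. The simulated column is 20,000 null trials per correlation with arms of 15, 30 and 30, using t on 72 degrees of freedom.

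| r | SE ratio | Type I error, approximate | Type I error, simulated |
|---|---|---|---|
| 0.3 | 0.908 | 7.5% | 7.2% |
| 0.5 | 0.935 | 6.7% | 6.6% |
| 0.7 | 0.962 | 5.9% | 5.8% |
| 0.9 | 0.987 | 5.3% | 5.3% |

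With normal critical values the simulated figures are 7.7%, 7.1%, 6.2% and 5.7%. The intercept variance reached zero in 83% to 100% of the trials.

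**Same option, other covariance.** Under compound symmetry that permits negative correlation, the model SE equals the change-score SE (ratio 1.000 at r = 0.3, 0.5 and 0.7). With an unstructured covariance the baseline residual can be driven to zero and the likelihood degenerates.

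**Option not taken.** Type I error is 4.9% to 5.1%. In a randomised contrast the change-score variance is proportional to 2(1−r) and the ANCOVA variance to 1−r². Their ratio is 2/(1+r).

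| r | Change / ANCOVA variance | ANCOVA variance lower by | 0.65 × √[(1+r)/2] |
|---|---|---|---|
| 0.3 | 1.54 | 35% | 0.52 |
| 0.5 | 1.33 | 25% | 0.56 |
| 0.7 | 1.18 | 15% | 0.60 |
| 0.9 | 1.05 | 5% | 0.63 |

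The last column applies if 0.65 is in units of the SD of change. It is the bound at which ANCOVA would have the power that the change score has at 0.65. It illustrates the gain and is not a proposal to move the bound. The plan does not say which SD it means.

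**Stratification factors.** Main effects of sex and statin use cancel from within-patient change, so adding them alters the time-by-treatment SE by 0.000. In ANCOVA, 30 versus 30 with assumed stratum effects of 0.2 to 0.5 SD, they alter the SE by less than 1%.

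**Non-randomised controls.** Suppose the control group differs from a training arm by a stable amount g at both visits, with no training effect. ANCOVA then carries a bias of (1−r)g. For g = 0.5 SD this is 0.25 SD at r = 0.5 and 0.15 SD at r = 0.7. Simulated type I error (30 versus 15) is about 14% and 10%, against about 5% for the change contrast. For g = 0.3 SD, ANCOVA gives about 8% and 6.5%. The gap g is an assumption, and other patterns of confounding could favour ANCOVA.

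**The case against.** The strongest reply is that the plan commits only to the time-by-treatment test, which is valid, and mentions baseline adjustment merely as a possibility. That stands: a reader might infer that the model will use baseline twice, but the text does not say so. The defect is an unresolved option.

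A reader might also infer that double use always makes the standard error too small. It does so only if the covariate is added and the random-intercept variance is bounded at zero. The plan specifies no covariance structure, and one that permits negative correlation removes the problem. At r = 0.9 the effect is small in any case.

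A third tempting reading is that omitting sex and statin use also makes the standard errors too small. The calculation shows it does not. These are design strata only for IMT versus aerobic, not for the control contrasts to which the quoted sentence belongs.

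Finally, the precision argument could be read as a case for ANCOVA throughout. The documents do not support that, because the controls are recruited separately. There, ANCOVA and change can differ in expectation, so the choice is a trade-off. It is also fair that this is a pilot sized on a t-test, and that a two-visit mixed model keeps patients who miss the second echo.

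What remains is that the option brings no benefit under any covariance structure, and that the randomised contrast forgoes precision available from data already collected.

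**Conclusion.** The concern holds in limited form. The wording permits baseline as both response and covariate. Using it that way cannot change the estimate. In a zero-bounded random-intercept fit, it understates the standard error by about 9% at r = 0.3, 4% at 0.7 and 1% at 0.9. Without the option, the analysis is valid but less precise than baseline adjustment in the randomised contrast: ANCOVA variance would be 35% to 5% lower over r = 0.3 to 0.9.

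These sizes rest on assumed correlations and equal variances at the two visits. The 0.91 SD and 0.65 SD power figures reproduce and are not challenged.

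**What to change.** 1. Delete the option of adjusting for baseline in a model whose responses include baseline.
2. For the randomised IMT-versus-aerobic non-inferiority contrast (part c), specify a two-visit mixed model with a common baseline mean and unstructured covariance, or ANCOVA of the 12-week value on baseline. Include sex and statin use because they are the randomisation strata; expect only a small gain from them.
3. For the contrasts with controls (parts a and b), prespecify one model that uses baseline once, for example the time-by-treatment model without the baseline covariate, and state its covariance structure. Report ANCOVA with baseline, sex and statin use as a sensitivity analysis. Describe these terms there as potential confounders, since the controls are not randomised.

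The cost is wording in the statistical section, with no new data or patients. ANCOVA drops patients with no follow-up echo; the common-baseline model keeps them, which favours it for part c.

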- We hypothesize that exercise training will result in a decrease in left ventricular end-diastolic and end-systolic volume and increase in ejection fraction as well as regional longitudinal strain (measures of morphology and systolic performance) as compared to the control group.
- We hypothesize that exercise training will increase mitral annular early diastolic velocity (e') as well as decrease the ratio (E/e') of early mitral inflow velocity (E) and e' (measures of diastolic performance).
- We hypothesize that both forms of training will be more beneficial compared to the control group and IMT will be non inferior to aerobic training regimen as related to cardiac remodeling.

Aim 2. To explore the association between cardiac remodeling and quantitative exercise training endpoints.

- We hypothesize that exercise training related central cardiac improvements (indicated in Aim 1) will lead to improved aerobic functional parameters (measured as peak VO_2 and VE/VCO_2 slope)
- We hypothesize that exercise training-related central cardiac improvements (indicated in Aim 1) will lead to improved quality of life (QoL) and symptom reduction (as measured by questionnaires).

Exploratory Aim: To explore the independent impact of cardiac morphology and pumping parameters on physical function, QoL, and symptom reduction. We hypothesize that when the outcomes of this proposal and the Merit are evaluated in combination that the improvements in cardiac morphology and function will lead to improvements in function, QoL and symptoms independent of peripheral skeletal muscle and vascular dynamics that will be collected as part of the Merit.

Background and Significance

Scope of the problem; high prevalence of HF and relevance of exercise intolerance

Prevalence of Heart Failure (HF) is rising, particularly due to the high incidence of HF among today's expanding population of older adults¹. Whereas mortality from coronary artery disease, sudden death, and other cardiovascular illnesses has declined, an expanding population is surviving into its senior years when they are paradoxically more susceptible to developing HF⁷. HF prevalence is already over 5 million in the US, and incidence (already 500,000 cases a year) is growing. It is the chief reason adults aged 65 and older are hospitalized, with annual costs exceeding 40 billion dollars a year.

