Project Time Line

Year I →→→→→	Year II →→→→→
Start Recruiting	Continue Recruiting
Start Assessments	Assessments
Start EX sessions	Exercise Sessions
	Manuscript Preparation

Year	Year 1		Year 2	
Time frame	0-6M	6-12M	12-18M	18-24M
Staffing	ES, RA, EX	ES, RA, EX	ES, RA, EX	ES, RA, EX
Enrollment	15	20	20	10
What will be happening	Setup/purchase supplies/recruitment/initial assessment /	Recruitment/assessments/interventions	Recruitment/Assessments/interventions	Recruitment/Assessments/interventions / manuscripts preparation

Study Team: Throughout the trial, [name] will meet regularly with co-investigators (4 times a year initially, and increasing to monthly when data analysis begins). Drs. [name], [name], [name], [name], [name], [name] all work in the VA or within close proximity and can presumably come to the VA campus for these meetings. However, phone teleconferencing will also be available for those who cannot participate in person. The skillsets and backgrounds of the investigators (as detailed in their biosketchs and the budget section) are extremely complementary and have contributed to a collegial and productive dynamic.

All study staff that will be working on this project are currently on staff at the VABHS. The echo sonographer, research assistant, and exercise physiologist will be an integral part of the team, they will coordinate recruitment, participant screening, enrollment, perform assessment visits, and follow ups. The current VABHS infrastructure through the Clinical Studies Unit (CSU) provide the ability for one exercise physiologist to perform the functional assessment while another performed the exercise trainings. This will allow this physiologist to remain blinded to the subject's intervention group thus eliminating tester bias.

Statistical Analysis: General considerations: This is a pilot study, described below are continuous outcome measures, primarily changes in function outcomes and gene expression and either continuous or categorical predictors. In all instances, outcome variables will be evaluated for violation of model assumptions and transformation of these variables will be considered as a remedy if needed. Analyses will generally be performed with an intent-to-treat approach, with sensitivity analyses performed to assess the role of drop-outs on the results.

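### The Aim 2 model relates outcome levels to echo levels at the same visits, so it can be significant when within-patient cardiac change has no effect on function

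*Combined protocol and SAP*

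**What the plan says.** Under Specific Aims, Aim 2 is framed as exploring an association, but its first hypothesis is about change: "We hypothesize that exercise training related central cardiac improvements (indicated in Aim 1) will lead to improved aerobic functional parameters". The Statistical Analysis section repeats this: "We hypothesize that exercise training related cardiac improvements will lead to improved aerobic functional parameters".

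The model given there for Aim 2 uses levels. On the outcome side, "baseline and follow-up in peak VO_2 , VE/VCO_2 slope and quality of life will be the outcomes in separate mixed linear regression models". On the predictor side, these models are fitted "using the measures of morphology, systolic and diastolic performance at evaluation times that were used as outcomes in aim 1 as predictors". For this aim the text names no change score, baseline echo term, visit term, arm term or separation of within-patient from between-patient variation.

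Two nearby statements matter for comparison. For Aim 1 the same section does specify a change contrast: "specifically the interaction between time and treatment, with the ability to adjust for baseline values of the outcomes". The general considerations describe the analyses this way: "described below are continuous outcome measures, primarily changes in function outcomes and gene expression and either continuous or categorical predictors".

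The Exploratory Aim fits the Aim 2 outcomes "using the predictors from aim 1 with the addition of potential confounders of peripheral function", and says the result will show the independent effect of central cardiac change.

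Sample Size and Power sizes Aim 2 by a joint test: "a mixed linear regression model with 7 predictors would result in a detectable R^2 of 0.19", against a null model, with 80% power, alpha 5% and 75 subjects.

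**The concern.** A random intercept allows for correlation between a patient's two visits, but it still gives each echo measure a single slope. That slope is a weighted average of a between-patient association and a within-patient association. If patients with better hearts are fitter at both visits, the slope is non-zero even when a change in the heart does nothing for fitness. Some patient-level correlation is plausible here, because the inclusion criteria run from AHA stage B to NYHA class III.

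A significant Aim 2 result could then be reported as remodeling driving functional gain when it only restates that sicker hearts go with lower fitness. The dissemination plan centers on mechanism and on the relative contribution of central and peripheral effects, so this is the conclusion readers would look for.

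**Working it through.** **1. The plan's own figure.** Inputs from Sample Size and Power: 7 predictors, R² = 0.19, n = 75, alpha 5%. Overall F test with 7 and 75 − 7 − 1 = 67 df:

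- f² = 0.19 / 0.81 = 0.235
- noncentrality = f² × 67 = 15.7, giving power 79.4%
- R² detectable at exactly 80% power = 0.192

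The stated 0.19 reproduces. Other conventions give 0.175 (noncentrality f² × 75) or 0.181 (random predictors). The calculation counts one record per patient.

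**2. What the slope estimates.** Take two visits, with visit-to-visit correlation ρx for the echo measure and ρy for the outcome. The visit sum carries the between-patient information and the visit difference carries the within-patient information. The weights are approximately

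between : within = (1 + ρx)/(1 + ρy) : (1 − ρx)/(1 − ρy)

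| ρx | ρy | Between-patient weight, formula | Simulated |
|---|---|---|---|
| 0.8 | 0.8 | 1/(1 + 1) = 0.50 | 0.50-0.56 (equal correlations) |
| 0.8 | 0.9 | 0.947/(0.947 + 2) = 0.32 | 0.34 |
| 0.9 | 0.8 | 1.056/(1.056 + 0.5) = 0.68 | 0.69 |
| 0.7 | 0.95 | 0.872/(0.872 + 6) = 0.13 | 0.14 |

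With equally stable measures the two parts carry about equal weight.

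**3. Hand check, one predictor, no within-patient effect.** Use unit variances, ρx = ρy = 0.8, and correlation r between the stable patient-level parts.

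- Between-patient slope = 2 × r × 0.8 / 1.8, which is 0.267 at r = 0.3
- Fitted slope ≈ 0.5 × 0.267 = 0.133
- Standard error ≈ 1/√(2 × 75) = 0.082
- z ≈ 1.63, so significance in about 37% of trials

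At r = 0.5 the slope is 0.222, z ≈ 2.72, and the rate is about 78%.

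**4. Simulation.** 75 patients, two visits, random intercept, visit term included, within-patient effect zero, equal visit-to-visit correlations of 0.8 and 0.9, 2,000 trials per cell. The seven predictors were given an assumed mutual correlation of 0.3.

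| Patient-level r or multiple R | One predictor | Seven predictors, joint test |
|---|---|---|
| 0 | 5-6% | 7% |
| 0.2 | 20-23% | 14% |
| 0.3 | 41-46% | 21-22% |
| 0.4 | 61-71% | 36-39% |
| 0.5 | 84-87% | 56-62% |
| 0.6 | 95-97% | 76-84% |

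Extending the visit-to-visit correlation down to 0.7 widens the joint-test ranges to 16-25% at 0.3 and 39-66% at 0.5, and the one-predictor ranges to 34-46% and 70-90%. The 7% at zero is small-sample inflation of the likelihood-ratio test. With unequal stability the one-predictor rate at r = 0.3 is 32% (ρx 0.8, ρy 0.9), 15% (0.7, 0.95) or 55% (0.9, 0.8).

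**5. Do visit and arm terms cure it?** With visit, arm and their interaction added (one predictor, visit-to-visit correlation 0.9, 400 trials), the rate is still 42% at r = 0.3 and 88% at r = 0.5. The within-patient coefficient in the split model gives 5.5% and 6.3% (simulation error about 1 point).

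**6. Do the alternatives hold their level?** Testing the deviation after splitting into patient mean and deviation gives 4.7-5.9% for one predictor. For seven it gives 7-8% by likelihood ratio, the same small-sample inflation as above. Simple change-on-change with an F test gives 4.2-6.1% throughout. Its detectable R² is 0.192 at n = 75 and 0.203 at n = 71 (5% attrition, the rate the Limitations section cites from a previous trial).

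**The case against.** The best defense is that this is a pilot, that both statements of Aim 2 say it is to explore, and that the general considerations mention changes in function, so the authors plainly had change in mind. The Aim 1 treatment comparisons are untouched. The short Aim 2 text is also thin specification: not naming visit or arm does not exclude them. All of this stands and lowers the severity. It does not remove the point, because no section carries change into the Aim 2 predictors, and visit and arm terms alone leave the rate almost where it was.

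Several stronger readings are tempting and are not supported:

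- *The cross-sectional part dominates.* Not in general. With equal stability the split is about even, and if the outcome is the more stable measure the within-patient part has more weight.
- *The one-predictor rates are the plan's error rate.* The plan is powered on a joint test of seven predictors, for which the rates are lower. Multiple R and a single r are also different scales.
- *The power figure is wrong.* It reproduces. The issue is what that R² measures.
- *Redundant predictors invalidate the test.* Materials and Method lists seven indices, among them EF, which is computed from the two volumes, and E/e', which contains e'. Collinearity would blur individual coefficients, but it does not bias a joint R² test, and Aim 2 never lists its seven predictors.

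**Conclusion.** The point holds in this form: followed as written, the Aim 2 model does not isolate the association its hypothesis describes, and a significant result can arise when within-patient cardiac change has no effect. The false-positive rate of the joint test is roughly 16-25% at a patient-level multiple R of 0.3 and 39-66% at 0.5, against a nominal 5%.

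These sizes assume equal visit-to-visit correlations of 0.7 to 0.9 for echo and outcome, and complete data on 75 patients. The direction depends only on the patient-level correlation not being zero; the size moves with relative stability, as the 15% and 55% cells show. The Exploratory Aim inherits the problem and is more exposed in wording, since it claims to isolate cardiac change.

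A reader might infer that Aim 2 must be repaired before the trial's results can be used. The documents do not support that, given the exploratory status of the aim and the unaffected Aim 1 comparisons. It should be fixed before analysis.

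**What to change.** For each Aim 2 and Exploratory Aim outcome, replace each echo measure by two terms: the patient's mean over the two visits, and each visit's deviation from that mean. Include visit and arm. Name the joint test of the deviation terms as the test of the hypothesis, with an F or other small-sample reference distribution. Simple change-on-change regression is an acceptable alternative; there the intercept is the visit effect and an arm term corresponds to visit-by-arm.

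Do not treat baseline-plus-change, or change-on-change adjusted for both baselines, as the same test. Given the baseline value, a larger change in a noisy measure partly reflects a higher true patient level, so some between-patient association leaks back. In simulation these versions gave 7.6-8.5% false positives at r = 0.5, and up to 9-10% in other runs.

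State that the detectable R² of 0.19 is then a share of the variance of change; arm terms will alter it slightly. As a secondary improvement, list the seven predictors.

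The cost is SAP wording and a recoded dataset, with no new data. The test will be less likely to reach significance, because it no longer borrows the cross-sectional correlation. A within-patient association would still not prove that cardiac change causes functional change, and the SAP should say so.
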